**D. SAMPLE SIZE AND DATA ANALYSIS**

If you are uncertain about how to calculate your sample size and determine appropriate data analysis, please contact the Epidemiology and Biostatistics Core at [[contact]](mailto:[contact]) for assistance in completing this section.

*If this is a case series based only on the patients available and only descriptive statistics will be obtained, state this in lieu of a sample size calculation. However, if you propose a case series, but plan hypothesis testing (e.g., the calculation of p-values using statistical tests) you need to estimate your*

**Sample Size – Support estimates with evidence from the literature or prior studies and perform an appropriate sample size calculation.**

Proposed analysis (e.g., student's t-test, ANOVA, chi-square, regression, etc.):

Outcome variables of interest are all continuous. Two-sample t-test and multivariate linear regression will be utilized if the data is normally distributed; otherwise Mann-Whitney U test (non-parametric equivalent to the two-sample t-test) will be utilized.

1. Alpha level: 0.05
2. Beta or power level: 0.82
3. Primary outcome variable estimate (mean +/- s.d. for continuous outcome, frequency/percentage for categorical variable):

The primary outcome will be the calculated total blood loss, summarized as mean +/- s.d. Based on historical data of patients that underwent PAO or PAO/Scope without IV TXA, the mean calculated blood loss was approximately 1296 mL with a standard deviation of 383.27 mL.

4. Number of groups being compared (use 1 for paired analysis within the same subjects):

Two groups will be compared: treatment arm (up to 1 g of IV TXA diluted in 50 mL of normal saline) versus those receiving placebo (50 mL of normal saline)

5. Effect size or change expected between groups: 250 mL difference in blood loss
6. Resulting number per group: 40 per group
7. Total sample size required: 80

**Data Analysis - describe how the primary outcome will be analyzed and what types of statistical calculations will be used. Do the same for each secondary outcome. Reiterate briefly the main analysis to be done, which groups, which variables, possible confounders. Address how possible confounders will be identified and handled in the analysis.**

The primary outcome, calculated total blood loss, will be presented as mean +/- standard deviation and compared between the TXA and placebo arms with a two-sample t-test. Multiple linear regression will also be used to compare total blood loss volume between arms after adjustment for age, sex, BMI, and anesthesia type.

Calculated total blood loss will be determined from the difference between the preoperative hemoglobin and the lowest postoperative hemoglobin during the hospital stay (or the lowest

postoperative hemoglobin prior to transfusion). Based on hemoglobin balance, the estimated blood loss will be calculated according to the formula by Nadler et al. [19]:

$$\text{Estimated Blood Volume (EBV)} = (k_1 \times \text{Height}^3 \text{ (m)}) + (k_2 \times \text{Weight (kg)}) + k_3$$

For men,  $k_1 = 0.3669$ ,  $k_2 = 0.03219$ , and  $k_3 = 0.6041$

For women,  $k_1 = 0.3561$ ,  $k_2 = 0.03308$ , and  $k_3 = 0.1833$

Multiplying the EBV by the hematocrit (Hct) gives the red blood cell (RBC) volume. As such, a change in the RBC volume can be calculated from a change in the Hct level [20, 21]:

$$\text{Total RBC volume loss} = \text{EBV} \times (\text{Hct Preop} - \text{Hct Postop})$$

Transfusions (mean volume per unit, mL) can be taken into account by calculating the total blood loss:

$$\text{Total blood loss (L)} = \text{Total RBC volume loss} + (\text{No. of Units Transfused} \times 0.285) / (\text{Hct Preop} - \text{Hct Postop}) / 2$$

Continuous secondary outcomes (postoperative allogeneic blood transfusion, intraoperative cell saver utilization, and length of hospital stay) will be analyzed in the same manner as the primary outcome.

The incidence of complications will be reported as proportions and 95% confidence intervals.

All hypotheses will be evaluated with two-sided tests with statistical significance set at  $\alpha = 0.05$ .

The authors will create a data safety monitoring board (DSMB) that will meet once a quarter to capture any complications, including but not limited to death, DVT, PE, and wound complications. This will include anesthesia, surgical, nursing, and research representatives. The time frame for reporting adverse events will be 1 week. If any mortality is seen, or any increase in DVT or PE rates from the established incidence in the literature, the study will be stopped. The senior author and principal investigator will contact the IRB directly if any of the above occurs. In accordance with the Hospital guidelines for TXA use, DVT, PE, stroke, transient ischemic attack (TIA) and myocardial infarction (MI) will be reported to the Department of Quality Management ([name]).

One planned interim analysis for efficacy will be performed after outcome data are collected on 50% of patients. The Haybittle-Peto boundary will be employed, where the DSMB will consider stopping the trial if the independent samples t-test comparing calculated blood loss volume between the TXA and placebo groups produces a p-value  $< 0.001^1$ . If the trial continues to completion, the final p-value threshold for significance will be the typical 0.05. No adjustment in sample size is necessary to account for the interim analysis.

Upon completion of the study, the results will be reported according to the CONSORT guidelines.

You have completed the Clinical Research Proposal for this study. The proposal should be submitted to the appropriate Clinical Review Panel (CRP) for scientific review. If you are unsure of which Clinical Review Panel to select, please contact [name] at [name].

 Pocock SJ. When (not) to stop a clinical trial for benefit. JAMA 2005; 294:2228-20.

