This trial will be registered on ClinicalTrials.gov. This All patients undergoing PAO by the study surgeon ([name]) will be identified in his office and screened for eligibility as potential patients for participation in the study. A research assistant will review the office and operative calendars of the study surgeon each week to identify and recruit potential patients. The assistant will record on the CONSORT diagram any reasons for ineligibility/exclusion.

b) *Who will obtain consent? When and where will consent be obtained? List the names and roles of all individuals who are designated to obtain consent.*

The surgeon, a co-investigator or research assistant will obtain consent prior to surgery, at the patient's preadmission screening visit. All authors on the protocol, in addition to their research assistants, will be designated to obtain consent.

c) *How many subjects will be enrolled? If controls are being used, state how they will be identified and consented.*

Wingerter, et al.[11] demonstrated that IV TXA may reduced post-PAO total blood loss by 314.4 mL (30.8%). A retrospective chart review of all PAOs performed by the PI at HSS found a mean  $\pm$  SD calculated blood loss of 1295.98 mL  $\pm$  383.27 mL. Studies in the total hip literature have defined 250 mL as a clinically important difference in blood loss [18]. Therefore, we will power the study to detect a 250 cc difference calculated total blood loss between groups. Our analysis shows that 40 patients are required in each arm of the study (80 patients total) to achieve 82% power with an independent-sample t-test and statistical significance set to alpha equal to 0.05.

d) *What age range will be used?*

Patients  $\geq$  12 years old will be screened for study eligibility.

**3. Interventions or Observations – what data are going to be collected and from what source? Be specific and describe the interventions or observations in detail. Answer each question individually**

*a) What are the procedures, treatments, and/or interventions, as well as sources of research material to be utilized, that will be part of this research project?*

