**Data recorded from outpatient postoperative office records will include:**

- Chart review of progress notes for evidence of clinically significant VTE
- Chart review of progress notes for evidence of reoperation, hematoma, seroma, or postoperative infection
- Chart review of progress notes for documentation of reoperation

c) *If controls are included in this proposal, please include the following: describe how they will be matched with the study subjects; state whether the controls will have identical data recorded, or describe any differences compared to the intervention subjects.*

Patients will be randomized to either the intervention or control group, as per randomization protocol described elsewhere in the proposal. For patients who are randomized to the control group, study data will be collected in the same manner as for the intervention group.

e) *Are all the tests or images part of standard of care? If not, identify which tests are not standard of care. What source of funds will be used to pay for them?*

All tests and imaging are considered standard of care.

e) *Create a data collection sheet and include all data/datafields to be collected. Include time points of data collection and final outcome time point. Attach the data collection sheet.*

Please see attached.

f) *Attach/upload all questionnaire(s) to be used. Provide information about the validity, reliability and appropriateness of the instrument(s) for your study.*

g) If randomization is involved, state how the randomization will be done, by whom, when, who will ensure randomization is carried out, and whether anyone will be blinded to the randomization group. Clearly explain the treatment arms of the study.

*Randomization Process:*

The patients will be randomized into one of 2 groups: (1) 10 mg/kg, up to a maximum of 1 g, of IV TXA (diluted in 50 mL of normal saline, with a maximum concentration of 100 mg/mL) or (2) 50 mL of normal saline prepared by the pharmacy. Assignment of patients will be made prior to the initiation of enrollment for the study. Patients will be randomized using a computer generated (SAS PROC) block randomization schedule to ensure equivalent numbers of patients in each group over the course of the study in case early stopping is required. Randomization will be stratified by sex and surgery type (PAO or Scope/PAO) so that the number of male patients and Scope/PAO patients will be balanced in each study group between trial arms.

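### Randomization is stratified by sex and surgery type, but the primary and interim t-tests use neither factor and no planned model contains surgery type

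*Combined protocol and SAP*

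**What the plan says.** - **Randomization (section C.3(g), Randomization Process).** "Patients will be randomized using a computer generated (SAS PROC) block randomization schedule". The schedule is stratified by sex and by surgery type (PAO or Scope/PAO), with the stated aim "so that the number of male patients and Scope/PAO patients will be balanced in each study group". The block size is not given.
- **Sample size (section C.2(c)).** 40 patients per arm "to achieve 82% power with an independent-sample t-test" at alpha 0.05, for a 250 mL difference and an SD of 383.27 mL. Section D says the SD comes from historical patients who had PAO or PAO/Scope.
- **Primary analysis (section D, Data Analysis).** Total blood loss is "compared between the TXA and placebo arms with a two-sample t-test". A multiple linear regression is planned in addition, "after adjustment for age, sex, BMI, and anesthesia type". Section D also names Mann-Whitney as the alternative if the data are not normal.
- **Interim analysis (section D).** At 50% of patients, the efficacy boundary is p < 0.001 from the "independent samples t-test comparing calculated blood loss volume between the TXA and placebo groups".

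Surgery type therefore enters no planned analysis, and no reason is given for leaving it out.

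**The concern.** Blocking within strata forces the arms to be nearly balanced on sex and surgery type. If these factors predict blood loss, the difference in means varies less from trial to trial than under simple randomization. An unadjusted t-test does not recognize this. Its standard error uses the total variance, including the between-stratum part that the design has removed from the comparison. The test is then conservative and its confidence interval is wider than it needs to be. The planning SD comes from a series mixing the two surgery types, so it includes any variance due to surgery type.

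At stake is efficiency in a trial that stops at 80 patients with no stated allowance for dropout. The direction of the treatment effect and the control of false positives are not in question.

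**Working it through.** **Inputs from the documents.** Difference 250 mL; SD 383.27 mL; 40 per arm; two-sided alpha 0.05; interim at 20 per arm with p < 0.001.

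**Assumptions, because the documents give no figures.** R², the share of blood-loss variance explained by sex and surgery type together, is set to 0, 0.05, 0.10 and 0.20. The main simulation uses blocks of 4, 20% male and 40% Scope/PAO.

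**1. The plan's own figure.** SE = 383.27 × √(2/40) = 85.70 mL. Noncentrality = 250/85.70 = 2.917. With 78 df the critical value is 1.991, and the noncentral t gives a power of 82.15%. The stated 82% is reproduced.

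**2. Both factors modelled, final analysis.** The residual SD is 383.27 × √(1 − R²), with 76 df (two more coefficients) and exact balance within strata. For example, at R² = 0.10 the SD is 363.6, the SE is 81.30, the noncentrality is 250/81.30 = 3.075, and the power is 85.9%.

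**3. True type I error of the t-test under exact balance.** The test divides by a standard error that is too large by the factor 1/√(1 − R²), so alpha ≈ 2 × [1 − Φ(1.96/√(1 − R²))].

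| R² | Exact power, adjusted | t-test true alpha (formula) |
|---|---|---|
| 0 | 82.12% | 0.050 |
| 0.05 | 84.0% | 0.044 |
| 0.10 | 85.9% | 0.039 |
| 0.20 | 89.6% | 0.028 |

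**4. Simulation of the actual randomization** (stratified blocks of 4, 10,000 trials per setting, R² split equally between the factors):

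| R² | Alpha, t-test / adjusted | Power, t-test / adjusted | Mean 95% CI width, t-test / adjusted (mL) |
|---|---|---|---|
| 0 | 0.053 / 0.053 | 82.1% / 81.9% | 341 / 341 |
| 0.05 | 0.044 / 0.049 | 82.9% / 84.4% | 340 / 332 |
| 0.10 | 0.039 / 0.049 | 83.2% / 85.5% | 341 / 323 |
| 0.20 | 0.030 / 0.048 | 84.7% / 89.7% | 341 / 305 |

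Results are similar if R² comes from sex alone or surgery type alone. At R² = 0.10, block sizes of 2 or 8 and other stratum shares (10% male with 20% Scope/PAO; 30% male with 50% Scope/PAO) give a t-test alpha of 0.035 to 0.043 and a gain of 2.2 to 3.0 points. A second simulation with 50% Scope/PAO agrees: 83.7% against 86.2% at R² = 0.10, and 84.6% against 89.5% at R² = 0.20. In it the spread of the estimate itself is almost the same with or without adjustment (SD about 81 mL either way at R² = 0.10). The gain thus comes from a correct standard error, not from a better point estimate.

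**5. Interim look.** SE = 383.27 × √(2/20) = 121.2 mL and noncentrality = 250/121.2 = 2.063. The exact chance of crossing p < 0.001 is 8.52% for the t-test at R² = 0 (38 df). With both factors modelled (36 df) it is 8.40%, 9.2%, 10.1% and 12.4% over the four R² values. The simulated t-test falls as R² rises: 8.8%, 8.0%, 7.8% and 7.0%.

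**The case against.** The strongest case against is that the plan breaks no promise. The t-test matches the power calculation, its power rises slightly with R², and it meets 82% in every scenario. That is true, and it is why this is an improvement and not a correction.

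Second, R² is unknown and the upper values need large differences. With difference = SD × √(R²/[p(1 − p)]), 20% male and 40% Scope/PAO, R² = 0.20 split equally needs gaps of about 303 mL by sex and 247 mL by surgery type. R² = 0.10 needs about 214 and 175 mL. The target treatment effect is 250 mL. Nothing in the documents shows that either factor is prognostic. Sex is plausible because it sets the coefficients of the blood-volume formula: at an assumed 1.70 m and 70 kg, that formula gives 4.66 L for men and 4.25 L for women. This objection stands as a limit on the size of the gain, which may be nil.

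Third, sex is already in the supporting regression. Going from sex alone to both factors adds about 1 to 2 points (85.0% to 86.2% at R² = 0.10; 87.3% to 89.5% at 0.20). But that regression is an additional analysis. The primary and interim decisions rest on the t-test.

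Fourth, the change touches other text: the Mann-Whitney fallback, the power statement, and the rule that continuous secondary outcomes follow the primary method. This is fair, and needs consequential edits only.

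Fifth, the interim boundary is deliberately hard to cross, so the gain there matters little in practice. That too is fair; the reason to change the interim test is consistency with the final one.

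**Conclusion.** The concern holds as an efficiency point. The plan balances two factors by design, uses neither in its primary or interim test, and puts surgery type in no model. There is no bias, no inflated error and no sample-size mistake.

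The gain depends on an R² the documents do not give. At R² of 0.05 to 0.10 it is about 1.5 to 3 points of power, with a 95% confidence interval about 8 to 17 mL narrower (340 to 332, and 341 to 323). At R² = 0.20 it is about 5 points and 36 mL (341 to 305). At R² = 0 there is no gain, and the exact cost is 82.15% − 82.12% = 0.03 points at the final analysis and 8.52% − 8.40% = 0.12 points at the interim. With so small a downside, the change should be made, but the trial is sound without it.

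**What to change.** 1. In section D, define the primary analysis, at interim and final, as a linear model of calculated total blood loss on arm, sex and surgery type (PAO or Scope/PAO). Report the adjusted mean difference in mL with its 95% confidence interval.
2. Add surgery type to the existing regression with age, sex, BMI and anesthesia type.
3. Keep the unadjusted t-test as a supportive analysis. The sample size need not change; note that 82% is the figure for the unadjusted test.
4. Make the consequential edits: say what replaces the model if normality fails, and whether the continuous secondary outcomes follow the new model.

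Make the change before any unblinded outcome data are seen, so that the choice of covariates cannot look data-driven. The cost is wording and two degrees of freedom. Both factors are known at randomization and no new data are needed.

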**Data recorded from the electronic medical record will include:**

- Date of surgery
- Patient age at the time of surgery
- Patient gender
- Patient height (cm) and weight (kg) at time of admission

- Transfusion requirement during inpatient stay (units required)
- Postoperative day and time of discharge
- Preoperative CBC data and coagulation study data
- Postoperative hemoglobin on all inpatient days postoperatively (g/dL)
- Chart review of progress notes for evidence of clinically significant VTE
- Chart review of progress notes for evidence of reoperation, hematoma, seroma, or postoperative infection

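### The supportive adjusted regression omits estimated blood volume and preoperative hematocrit, two baseline values that enter the endpoint and are already available

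*Combined protocol and SAP*

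**What the plan says.** Under Data Analysis in section D, the primary outcome is "compared between the TXA and placebo arms with a two-sample t-test". A second analysis follows, a multiple linear regression that compares the arms "after adjustment for age, sex, BMI, and anesthesia type". No reason is given for this choice of covariates.

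The same section, repeating Outcome Measures in section C, builds the endpoint. EBV is computed from sex, height cubed and weight. Then "Multiplying the EBV by the hematocrit (Hct) gives the red blood cell (RBC) volume", and red cell loss is EBV times the fall in hematocrit. A separate term for transfused units is added; as printed, EBV does not multiply it.

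The inputs are collected for every patient. The list of data from the electronic medical record in section C includes "Patient height (cm) and weight (kg) at time of admission" and "Preoperative CBC data and coagulation study data".

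**The concern.** EBV and preoperative hematocrit are fixed before treatment, enter the outcome formula directly, and cost nothing more to obtain. A covariate earns its place by explaining outcome variance, and these two are natural candidates. The model carries BMI instead, which is weight divided by height squared. Patients with the same BMI but different heights can differ widely in EBV.

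At stake is the precision of the adjusted estimate. If loss rises with body size, the residual variance is larger than it need be. A chance imbalance in body size between two arms of 40 would also be only partly corrected, because randomization is stratified by sex and surgery type but not by body size.

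**Working it through.** **1. The plan's own figure.** Inputs from section D: difference 250 mL, SD 383.27 mL, 40 per arm, alpha 0.05, two-sided. Noncentrality = 250 / (383.27 × √(2/40)) = 250 / 85.70 = 2.917. With 78 degrees of freedom the power is 82.1%, so the stated 82% reproduces. It involves no covariates.

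**2. Is BMI a stand-in for EBV?** The formula for women is 0.3561 × height³ + 0.03308 × weight + 0.1833. At BMI 25:

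- 1.55 m, 60.06 kg: 1.326 + 1.987 + 0.183 = 3.50 L
- 1.75 m, 76.56 kg: 1.908 + 2.533 + 0.183 = 4.62 L

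The ratio is 4.62 / 3.50 = 1.32, a 32% difference at equal BMI and sex.

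**3. How much of EBV do sex and BMI recover together?** The documents give no body-size distribution. Assumed: 10-30% male; mean height 1.64 m (SD 0.07) in women and 1.77 m (SD 0.075) in men; mean BMI 24 and 26, SD 3 to 5. In a simulation, sex and BMI explain about 61-78% of EBV variance. The omission is therefore partial.

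**4. What would adding EBV gain?** The outcome is scaled to mean 1296 mL and SD 383.27 mL. Residual SD = 383.27 × √(1 − R²), and power comes from the noncentral t with 78 − k degrees of freedom for k covariates. Central case: 20% male, BMI SD 4.

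| Assumed relation of loss to EBV | R², sex + BMI | R², with EBV | Cut in residual variance | Power |
|---|---|---|---|---|
| None | 0 | 0 | 0 | 82.1% both ways |
| Square root of EBV | 0.068 | 0.094 | 2.8% | 84.7% to 85.7% |
| Proportional to EBV | 0.286 | 0.396 | 15.3% | 92.6% to 95.9% |

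In the proportional case, across all assumed sex mixes and BMI SDs, the cut is 13.2-17.1%. Power goes from 88.5% to 92.4% at one end and from 95.2% to 97.8% at the other, a gain of 2.6 to 3.9 points. A slightly different assumed population (85% women, heights 1.65 and 1.78 m, BMI about 24) gives R² of 0.204 and 0.298. The cut is then 1 − 0.702/0.796 = 11.8%, and power goes from 89.8% to 93.0%. Overall the cut is 12-17%. In the proportional case R² is the same to three decimals whether EBV replaces BMI or is added beside it.

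**5. What does adding cost?** If the new covariates explain nothing, power is 82.10% with 4 covariates (74 df), 82.08% with 5 and 82.07% with 6. That is about 0.01 point for one added covariate and 0.03 for two.

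**6. What if BMI were dropped for EBV?** Suppose BMI itself predicts loss (assumed) and EBV matters only through BMI. Replacing BMI lowers power from 85.5% to 83.7% at a correlation of 0.3, and from 88.1% to 85.0% at 0.4. Adding EBV beside BMI avoids that loss.

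**7. The transfusion term.** Read literally, one unit at an assumed hematocrit drop of 0.10 adds 0.285 / 0.10 / 2 = 1.43 L. The red cell term at an EBV of 4.2 L is 4.2 × 0.10 = 0.42 L. If one third of patients receive one unit each (33.3% were transfused historically, section A; one unit each is assumed), sex and EBV explain about 1% of the variance of the endpoint as printed. Sex and BMI explain slightly less. The gains in step 4 therefore do not apply to the formula read literally.

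**The case against.** The strongest objection is that multiplication by EBV does not by itself make EBV prognostic. The formula converts a hematocrit drop into a volume. If a given absolute volume is lost, a larger EBV gives a smaller drop and the product is unchanged. EBV then predicts loss only if bleeding scales with body size, and the documents report no such correlation. This stands. A reader might infer from the formula alone that precision is being discarded; the documents do not support that.

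A reader might also infer that BMI is the wrong covariate and should be replaced. Step 6 shows that replacement is not free: if BMI has prognostic value of its own, the swap costs about 2 to 3 points. The documents cannot say which situation holds. This rules out a replacement but not an addition.

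Third, preoperative hematocrit has no calculation behind it. If the fraction of blood volume lost is independent of everything else, adding hematocrit leaves R² at 0.297. This also stands. Its case is that it enters the endpoint directly and costs almost nothing, not that a gain has been shown.

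Finally, no decisive analysis is touched. The primary comparison, the sample size and the interim stopping rule all rest on an unadjusted t-test. That is correct, and it limits the point to the efficiency of a supportive model.

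**Conclusion.** The point holds as a low-cost improvement to a supportive analysis. The adjusted model omits two baseline values that are built into the endpoint and already held, and sex with BMI stands in for EBV only in part.

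For the adjusted comparison, adding EBV gains between nothing and about 3 to 4 power points (12-17% of residual variance at the top), with about 1 point under square-root scaling. These figures rest on assumed sex mix, height, BMI and scaling of loss with EBV, none of which the documents give. They also presume an endpoint that the transfusion term does not dominate. The gain from preoperative hematocrit is unquantified.

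A reader might infer that the trial's main result is biased or underpowered. It is not: the t-test, its 82% power and its type I error do not depend on these covariates.

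**What to change.** In section D, Data Analysis, prespecify EBV (or height and weight) and preoperative hematocrit as added covariates in the regression, keeping age, sex, BMI and anesthesia type. Fix the list before the interim analysis, so that the choice cannot follow unblinded data.

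Clarify the bracketing and denominator of the transfusion term in sections C and D first. The sponsor can then estimate the actual gain from its 93 historical cases instead of quoting the ranges above.

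The cost is a line of text, no new data, and one or two degrees of freedom (three if height and weight are entered separately).
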